5. SUBJECT ENROLLMENT

- a. Enrollment of subjects: Subjects will be approached for enrollment at the time of the first visit with a breast surgeon after their definitive breast biopsy. Clinical documentation of the subject consent and enrollment will be included in the dictated note.
- b. Breast tumor specimen collection:
 - i. Extra biopsy tissue blocks will be requested after subject registration, for IHC staining from the initial biopsy specimen.
 - ii. At the time of the lumpectomy or mastectomy, two additional portions of tumor not required for pathological diagnosis will be formalin fixed and paraffin embedded and flash frozen.

6. TREATMENT PROCEDURES

- a. Simvastatin will be obtained from commercial sources and will be provided free of charge to the participant through the KCI pharmacy. Participants will take simvastatin 20 mg daily for at least 2 weeks and no longer than 4 weeks, from the time of consent to the day prior to their definitive breast surgery. A pill diary will be maintained through the clinical trials office.
- b. Serum total cholesterol (TC), low-density-lipoprotein cholesterol (LDL-C) and high density lipoprotein cholesterol (HDL-C) will be measured in the KCI tissue core lab (PI [name]) at study entry, and at the end of statin administration. Pathology slides and tissue block material will be obtained from clinical pathologic material not needed for clinical purposes from the biopsy specimen and lumpectomy or mastectomy specimen.
- c. Participants will be monitored for toxicity through telephone monitoring and clinic visits as needed. Telephone monitoring will occur 3-5 days after initiating simvastatin and within 2 weeks of stopping simvastatin. Details about reported side effects will be maintained by the study nurse.
- d. Participants will be provided a \$25 Target gift card after the completion of all study related activities.

7. STUDY PROCEDURES

a. CANDIDATE BIOMARKERS

i. Tissue Markers

1. Ki-67 is a marker of breast tumor proliferation and will be the primary marker of interest.
2. Other markers of breast tumor proliferation will include cyclin D1, and P27.
3. Cleaved caspase-3 (CC3) is a marker of apoptosis.
4. C-reactive protein (CRP) is a marker of inflammation.
5. Cholesterol metabolism (HMGCoAR)
6. Composition of the plasma membrane: Lipid rafts
7. Activation of signaling markers (pAkt, pMAPK, pEGFR, pHER2)
8. Intra-tumoral levels of CYP2A1
9. ER, PR and HER2neu (clinical pathology laboratory)

ii. Serum Markers

1. Total cholesterol (TC)
2. Low-density-lipoprotein cholesterol (LDL-C)
3. High-density-lipoprotein cholesterol (HDL-C)
4. Serum 27-hydroxycholesterol

b. LABORATORY METHODS

c.

- i. Immunohistochemistry (IHC): IHC will be performed using well established protocols. Percent positive cells will be compared between the pre-surgical biopsy and the surgical resection using 3D Histotech software. Specifically, to assess the changes in tumor growth a standard marker of cellular proliferation, Ki67 will be utilized. Common markers of breast tumors that define treatment course will also be analyzed by IHC. Concentration and localization of ER α , PR, HER2 as well as intra-tumoral expression of CYP27A1 also will be assessed. To determine the concentration and localization of cholesterol in the tumor specimens, labeled-cholera-toxin B will be utilized. From these studies we expect to find that Ki67 will be reduced in the surgical specimen compared to the biopsy specimen. In addition, we would expect that the cholesterol detected in the cell would be reduced. If cholesterol is reduced, we would expect to see a differential activation of key signaling molecules including HER2, EGFR, Akt, and MAPK (if expressed).
- ii. HMGCoAR activity will be measured in tumor specimens via an in vitro assay that assesses the ability of a specimen to reduce HMGCoA into mevalonate and coenzyme A. Protein will be isolated from flash-frozen tumor specimens and utilized as the source of enzyme for this biochemical assay. Readout for the assay is a

change in spectrometric counts over time. From these experiments, we expect for the first time, to see a reduction in HMGCoAR activity in the surgical tumor specimen when compared with the biopsy specimen.

- iii. 27OHC: We will utilize the laboratory at the Baylor College of Medicine to assay 27OHC on serum using a modified isotope-dilution gas chromatography-mass spectrometry (GC-MS) method (52;52). Briefly, lipids will be extracted from the serum using a modified Folch technique. Oxysterols will be purified from other lipids by solid-phase extraction followed by derivatization and analysis by gas chromatography- mass spectrometry (GC-MS) on an Agilent 5973 (Agilent Technologies, Santa Clara, CA). In a prior analysis of 27OHC in the Women's Health Initiative, the inter-assay coefficient of variance was 16.6% and intraclass correlation of 55 blind duplicates was 0.47 (52). Analyses will be run in batches. Ten percent blinded duplicates will be included and between run coefficients of variation will be computed. We will use 250 ul aliquots from the archived KCI bio-repository for the analysis. uSerum levels of TC, LDL-C and HDL-C will be conducted in the laboratory of [name] at the KCI.

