3. EXPERIMENTAL PLAN

We will use a phase II "window of opportunity" design in which women with clinical stage 0 insitu or stage I or II invasive breast cancer will be enrolled during the time period between their definitive breast cancer diagnosis after core needle biopsy and the final surgical removal of their tumor. At the Karmanos Cancer Center (KCC), the majority of women with newly diagnosed stage 0 insitu and stage I and II invasive breast cancer are evaluated in the Walt Multidisciplinary Breast Clinic at the Detroit campus of the KCC or at the Weisberg cancer treatment center in Farmington Hills, MI. The majority of women with newly diagnosed breast cancer are scheduled for definitive

surgical resection within approximately 4 weeks of their initial diagnosis. All participants in this window of opportunity study will be provided a dose of simvastatin 20 mg for at least 2 weeks and no longer than 4 weeks in the interval between biopsy and definitive surgery. Simvastatin is one of the most commonly prescribed statins and is a lipophilic, high-potency statin, making it a reasonable candidate statin for this study. Simvastatin will be provided free of charge to the participants by the investigator through the KCI pharmacy. We will analyze both pre- and post-treatment biopsy/tumor specimens for markers of breast tumor proliferation, apoptosis, cholesterol metabolism, cell signaling and intra-tumoral expression of CYP27A1 and will analyze tumors as well for standard markers of breast cancer prognosis (ER, PR, HER2neu and tumor grade). This study will be conducted at the KCC (Walt Center and Weisberg and other Network Centers including Flint and Bay City) as well as Ascension Providence Hospital and the Henry Ford Health Systems as the clinical sites. As part of the protocol we will collect pre and post-surgical blood specimens to measure serum levels of total cholesterol (TC), high density lipoprotein cholesterol (HDL-C), low-density lipoprotein cholesterol (LDL-C) and 27-hydroxycholesterol (27OHC). The pre-surgical blood specimen will be obtained at the screening visit and the post-surgical blood specimen will be collected up until the first post-operative visit.

4. SUBJECT ELIGIBILITY:

a. Inclusion Criteria

- i. Provision of informed consent prior to any study specific procedures.
- ii. Female patients must be > 18 years of age.
- iii. Histologic confirmation of insitu or invasive breast cancer with any measures of ER, PR and HER2neu.

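### The biopsy-versus-surgery HMGCoAR activity comparison has no described pre-treatment frozen tissue, and Section 11 gives two subgroup lists that do not match

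*Combined protocol and SAP*

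**What the plan says.** **Activity assay.** Section 7, Laboratory Methods ii, specifies frozen input: "Protein will be isolated from flash-frozen tumor specimens and utilized as the source of enzyme for this biochemical assay". The investigators expect "to see a reduction in HMGCoAR activity in the surgical tumor specimen when compared with the biopsy specimen". Section 3 also commits to paired tissue in general terms: "We will analyze both pre- and post-treatment biopsy/tumor specimens for markers of breast tumor proliferation, apoptosis, cholesterol metabolism, cell signaling". The Section 7 marker list puts HMGCoAR under cholesterol metabolism.

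**Tissue collected.** For the biopsy, Section 5(b)(i) says: "Extra biopsy tissue blocks will be requested after subject registration, for IHC staining from the initial biopsy specimen". Section 6(b) adds: "Pathology slides and tissue block material will be obtained from clinical pathologic material not needed for clinical purposes from the biopsy specimen". For surgery, Section 5(b)(ii) takes two extra portions of tumor that "will be formalin fixed and paraffin embedded and flash frozen".

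**Timing.** Section 5(a): "Subjects will be approached for enrollment at the time of the first visit with a breast surgeon after their definitive breast biopsy". Inclusion criterion i in Section 4 requires: "Provision of informed consent prior to any study specific procedures".

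**Subgroups.** The tertiary objective in Section 11 names HMG-CoA (the documents' shorthand for the reductase), ER/PR, HER2neu and tumor grade. The power text in the same section names the same factors and gives Kruskal-Wallis as the test. The subgroup sentence of the Statistical Analysis Plan paragraph names lipid raft, ER, PR, HER2neu and P53, also with Kruskal-Wallis tests.

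**The concern.** A pre/post comparison needs the same kind of specimen at both times. Here the assay needs frozen tumor, and the text provides for frozen tumor only after treatment. The laboratory could then report post-treatment activity but no change from baseline.

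The subgroup mismatch matters for a different reason. The trial sets out to replicate two earlier window studies (Section 2(e)). For Ki-67, Section 2(c) gives subgroup results from those studies for two factors only: grade (7.2% reduction in high-grade against 0.3% in low-grade tumors) and high HMGCoAR expression (68% reduction). For ER it gives a subgroup result on apoptosis only. The two factors missing from the analysis sentence are therefore the two with a prior Ki-67 signal. Two different lists also leave the choice of subgroups open until the data are in hand, although the plan says it wants to guard against inflated type I error.

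**Working it through.** No figure in the plan is contested, so the check sets the texts side by side.

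**1. Tissue for the activity assay**

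| | Before treatment | After treatment |
|---|---|---|
| Specimen | Diagnostic core biopsy | Lumpectomy or mastectomy |
| Form described | Left-over blocks and slides (Sections 5(b)(i), 6(b)) | Paraffin-embedded and frozen portions (Section 5(b)(ii)); slides and blocks (Section 6(b)) |
| Stated use | IHC | IHC and frozen-tissue assay (Section 7) |
| Frozen portion described | No | Yes |

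- Freezing is mentioned in two places only: the surgical collection in Section 5 and the assay input in Section 7.
- That the biopsy material is not frozen is an inference; no sentence says so. The timing supports it. Women are approached after the biopsy, and consent precedes study procedures, so the study cannot itself freeze part of that biopsy.
- No second pre-treatment biopsy is described. The Study Design paragraph of Section 11 places the first assessment just before statin treatment but names no specimen. The study summary and Sections 5 and 6 identify the pre-treatment tissue as diagnostic material.
- The status of the comparison: change in HMGCoAR activity is not in the Section 1 objectives or among the Section 11 endpoints. It appears as an expected laboratory result.

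**2. Subgroup lists, counting ER and PR separately**

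| Factor | Tertiary objective | Power text | Analysis sentence |
|---|---|---|---|
| HMG-CoA | yes | yes | no |
| ER | yes | yes | yes |
| PR | yes | yes | yes |
| HER2neu | yes | yes | yes |
| Tumor grade | yes | yes | no |
| Lipid raft | no | no | yes |
| P53 | no | no | yes |

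- Objectives and power text: 5 factors. Analysis sentence: 5 factors. Shared: 3. Omitted: 5 − 3 = 2. Added: 5 − 3 = 2. All factors named anywhere in Section 11: 3 + 2 + 2 = 7.
- Objective (c) in Section 1 and the summary in Section 2(e) agree with the tertiary objective. The study summary at the front names the same factors across two adjacent sentences.
- Lipid raft is item 6 of the nine tissue markers in Section 7. P53 is not among the nine, nor in the objectives, endpoints or laboratory methods. Outside the analysis sentence it appears only in the background (Sections 2(c) and 2(d)) and in reference titles.

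**3. Where the two parts meet**

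The objectives group women by HMG-CoA expression. The only HMGCoAR method described is the activity assay, and the only frozen tissue described is surgical. If that assay were used for grouping, women would be classified on tumor already exposed to a drug that inhibits the enzyme. No expression method or cut-off is given.

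**The case against.** The strongest reply is that the power text already supplies what the analysis sentence lacks. It names HMG-CoA and grade, the outcome (pre/post Ki-67 differences) and the test. That stands. A reader of the analysis sentence alone might infer that these two subgroups have no planned analysis; Section 11 as a whole does not support that. The defect is an inconsistency within one section.

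Three further inferences are tempting and go too far.

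- **That P53 will have no data.** Blocks from both times and an IHC platform exist. The IHC paragraph also fails to name cyclin D1, P27, CC3 and CRP, which Section 11 treats as IHC measures. The text supports only that P53 is unlisted and has no described method.
- **That no woman will have baseline frozen tissue.** A diagnostic site might hold frozen cores. The documents do not describe such a source, but they do not exclude one.
- **That a stated aim fails.** The activity change is not an objective or endpoint, and Section 3 promises paired analysis of cholesterol metabolism without specifying enzyme activity.

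It is also fair to say that the documents nowhere state that subgroups will be formed on treated tissue. The risk for HMG-CoA arises because no other method is given. HMGCoAR staining may simply be intended and unstated.

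**Conclusion.** Both parts hold, as matters to correct in the text. As described, the paired HMGCoAR activity comparison cannot be made, because no pre-treatment frozen source is named. This rests on reading the left-over diagnostic blocks and slides as not frozen, which the order of biopsy and consent supports, and it falls away if an existing frozen source is identified. In Section 11 the analysis sentence matches three of the five factors in the objective and power text, omits two and adds two, one of which (P53) is not listed for measurement anywhere. Whether P53 is a slip for another marker cannot be told from the documents. The consequences are confined to exploratory subgroup aims and one laboratory expectation. The primary Ki-67 analysis does not depend on either.

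**What to change.** 1. **Activity assay.** Name an existing pre-treatment frozen source. Failing that, label the assay surgical-specimen-only and descriptive, and remove the biopsy-versus-surgery activity claim. This gives up a comparison that has no described baseline.
2. **Analysis sentence.** List HMG-CoA, ER, PR, HER2neu and tumor grade, as in the objectives and power text. The number of factors stays at five.
3. **P53 and lipid raft.** Remove P53 unless it is added to the measured markers with a method. Keep lipid raft, which is a listed tissue marker, only if labelled as an additional exploratory factor. Keeping one of them makes six factors; keeping both makes seven.
4. **HMG-CoA grouping.** Define it by expression in the diagnostic biopsy. This works only if a biopsy-compatible expression method is stated (IHC, for example) with one cut-off fixed before analysis, so the two changes go together.

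Items 1 to 3 are wording, unless P53 is kept, which needs a laboratory method. Item 4 may need one additional stain on existing blocks, with its reading, if HMGCoAR IHC is not already intended. Fewer women may be classifiable where biopsy tissue is short. The plan already allows for insufficient tissue, at diagnosis or surgery, in as many as 10 of the 50 participants (10/50 = 20%).

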8. REMOVAL AND REPLACEMENT OF SUBJECTS

In the absence of treatment delays due to adverse events, treatment will be completed unless the patient experiences any one of the following:

- A change from early stage to locally advanced or metastatic at the pre-surgical restaging.
- Inter-current illness that prevents further administration of the treatment.
- Unacceptable adverse event(s) including severe myopathy.
- The participant decides to withdraw from the study.
- General or specific changes in the patient's condition that render the patient unacceptable for further treatment in the judgment of the investigator.

9. SAFETY DATA COLLECTION, RECORDING, AND REPORTING

Data and Safety Monitoring

1. Scheduled research meetings will be held monthly or more frequently depending on the activity of the protocol. These meetings will include the protocol investigators and research staff involved with the conduct of the protocol.
2. During these meetings the investigators will discuss:
 - Safety of protocol participants (adverse events and reporting)
 - Validity and integrity of the data (data completeness on case report forms and complete source documentation)
 - Enrollment rate relative to expectation of target accrual, (eligible and ineligible participants)

- Retention of participants, adherence to the protocol and protocol deviations
 - Protocol amendments
3. Data and Safety Monitoring Reports (DSMR) of the research meetings will be completed by the Study Coordinator and submitted to the Data and Safety Monitoring Committee monthly for review.
 4. The Barbara Ann Karmanos Cancer Institute, Data and Safety Monitoring Committee (DSMC) provides the primary oversight of data and safety monitoring for KCI Investigator-initiated trials.

Data Management

Clinical trial data will be captured in OnCore (Clinical Trial Management System) electronic data capture system.

Trial data entered in Oncore will be verified by source documentation. The eCRFs should be completed by within 10 business days of the availability of clinical documentation of a study visit. Data clarification and queries should be completed within 7 working days of notification.

A KCI CTO QA Monitor will monitor essential clinical trial data.

10. ADVERSE EVENTS

The most commonly reported adverse reactions (incidence $\geq 5\%$) in simvastatin controlled clinical trials are upper respiratory infections, headache, abdominal pain, constipation, flatulence, nausea, vomiting, dyspepsia and asthenia. Other side effects reported are diabetes mellitus, cognitive impairment, pruritus, alopecia, a variety of skin changes (e.g., nodules, discoloration, dryness of skin/mucous membranes, changes to hair/nails), dizziness, muscle cramps, myalgia, arthralgia, pancreatitis, paresthesia, peripheral neuropathy, anemia, erectile dysfunction, interstitial lung disease, hepatitis/jaundice, fatal and non-fatal hepatic failure and depression.

The incidence of myopathy, including rhabdomyolysis was $< 0.1\%$, myopathy (defined as unexplained muscle weakness or pain with a serum creatine kinase [CK] > 10 times upper limit of normal [ULN]). Rhabdomyolysis (defined as myopathy with a CK > 40 times ULN) is rare. Rarely hypersensitivity reactions are noted.

Drug interactions:

Concomitant use of CYP3A4 inhibitors, cyclosporine, danazol is contraindicated. If treatment with itraconazole, ketoconazole, posaconazole, voriconazole, erythromycin, clarithromycin is unavoidable, therapy with simvastatin must be suspended during that course. The risk of myopathy, including rhabdomyolysis is increased by concomitant

administration of cyclosporine or danazol, amiodarone, dronedarone, ranolazine, or calcium channel blockers such as verapamil, diltiazem, or amlodipine, colchicine, and gemfibrozil. Protease inhibitors, such as saquinavir and ritonavir increases pancreatitis risk. Concomitant administration of digoxin with simvastatin resulted in a slight elevation in digoxin concentrations in plasma. Patients taking digoxin should be monitored appropriately when simvastatin is initiated.

Statistical Power and Sample Size: Sample size for this pilot study was determined by issues of feasibility. It is estimated that there may be insufficient tissue sample on as many as 10 participants (either at diagnosis or definitive surgery); therefore, we will plan to accrue a total of 50 participants.

Although numerous statistical tests and estimation procedures are planned, it is desired to guard against inflated type I errors. In order to provide some protection, the sample size calculations below assumed type I error of 0.01.

In pilot data on 20 women with early stage breast cancer from our institution, mean percent positive Ki-67 was 11.0% with a standard deviation (SD) of 12%. If all 50 women have adequate tissue, we will be able to detect a 6 percentage point decrease in Ki-67 if the correlation between pre and post Ki-67 is moderate, with 85% statistical power, testing with 1% type I error (Table 1), If the dropout rate is 10% and the pre-post correlation is lower, then we will be able to detect a 9 percentage point decrease in Ki-67. Differences of that magnitude correspond to a moderate effect size and are likely to be of clinical importance.

Table 1. Detectable Pre/Post Differences
Assuming Mean Baseline Percent Positive Ki-67 = 11%, SD = 12%
Statistical Power = 85%, Two-sided Type I Error = 1%

N	Effect Size	Detectable	
		Pre/Post Difference	Pre/Post Correlation
50	-0.53	-8	0.2
50	-0.53	-6	0.5
50	-0.53	-4	0.8
45	-.56	-8	0.2
45	-.56	-7	0.5
45	-.56	-4	0.8
40	-.60	-9	0.2
40	-.60	-7	0.5
40	-.60	-5	0.8

Detectable differences were calculated under the same assumptions for comparison of pre/post Ki-67 differences between groups defined by expression of hydroxymethylglutaryl CoA reductase (HMG-CoA), ER/PR status, HER2neu, and tumor grade. There will be 85% statistical power to detect large differences using Kruskal Wallis tests.

Table 2. Detectable Effect Size for Comparison of Groups Defined by Biomarkers and Group Size

Power	Number in each group		
	12/28	16/24	20/20
80%	---	1.2	1.2
85%	1.4	1.4	1.4
90%	1.5	1.5	1.5

The predicted accrual rate for the study will be 2 participants per month. To account for potential slow accrual over holidays we will plan to complete study procedures within 2 years of opening the study.

Reference List

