In a pre-operative study of women with stage 0 and 1 breast cancer, fluvastatin (80 mg vs. 20 mg) was administered for 3-6 weeks between the time of initial diagnosis and up until the time of the definitive breast cancer surgery. Statin use was associated with a reduction in breast tumor proliferation (7.2% reduction in Ki-67 expression in high grade tumors vs 0.3% reduction in low grade tumors) and a preferential increase in tumor apoptosis in high-grade vs. low-grade tumors (60% vs. 13%) as well as ER-negative vs. ER-positive tumors (55% vs 28%) (48). In a similar study of atorvastatin 80mg administered for 2 weeks among women with stage I and II invasive breast cancer, there was a 7.6% reduction in Ki67 expression with a higher reduction of 68% noted among breast tumor samples that had high expression of HMGCoAR (49).

Other studies have focused on molecular explanations of the effect of statins In a study of murine xenografts, simvastatin stimulated production of a variant of the p53 transcription factor and diminished the potential to form bone metastases (50). Other evidence also implicates the p53 pathway. A 3-dimensional breast cancer cell culture model showed that mutant p53 up-regulated the mevalonate pathway to induce an invasive phenotype. Addition of simvastatin to the culture medium caused reversion to normal morphology, while the malignant phenotype persisted when both simvastatin and GGPP were present in the medium (51).

Borgquist et al suggested that the antiproliferative action of statins is due to an effect on cyclin D1 and p27, through up-regulated expression of the tumor suppressor p27 and down-regulated expression of the oncogene cyclin D1 in breast cancer. (52). In normal cells, progression through the cell cycle is controlled by the cyclin dependent kinases (CDKs), a family of serine/threonine kinases (53). The CDKs form complexes with their regulatory units, cyclins, thereby activating the CDKs, leading to phosphorylation of the cell cycle regulatory proteins that initiate and regulate progression through the different phases of the cell cycle (54). In breast cancer cells, the cell cycle control system is deregulated at multiple levels, leading to abnormal cell proliferation (55). Cyclin D1 is a vital regulator of the G1/S transition. The interaction of cyclin D1 with CDK4 and CDK6, leads to phosphorylation and thereby inactivation of the Rb-protein and its G1-maintaining

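### Table 2 prints one detectable effect for all three group splits at 85% and 90% power, which its own assumptions do not give, and never states that effect in Ki-67 points

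*Combined protocol and SAP*

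**What the plan says.** All of this is in Section 11, Statistical Power and Sample Size, unless noted.

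- On error rate: "the sample size calculations below assumed type I error of 0.01". The Table 1 header adds "Statistical Power = 85%, Two-sided Type I Error = 1" (percent) and "Assuming Mean Baseline Percent Positive Ki-67 = 11%, SD = 12" (percent). Table 1 uses pre/post correlations of 0.2, 0.5 and 0.8 and gives its results in percentage points.
- On the group comparisons: "Detectable differences were calculated under the same assumptions for comparison of pre/post Ki-67 differences between groups", where the groups are defined by HMG-CoA expression, ER/PR status, HER2neu and tumor grade. The next sentence is "There will be 85% statistical power to detect large differences using Kruskal Wallis tests".
- Table 2 gives effect sizes only, for the splits "12/28 16/24 20/20". The 80% row is blank / 1.2 / 1.2, the 85% row 1.4 / 1.4 / 1.4 and the 90% row 1.5 / 1.5 / 1.5.
- The analysis text of Section 11 plans Kruskal-Wallis tests and 95% confidence intervals for differences between groups. It defines ER, PR and HER2neu as positive or negative. It does not say how many grade levels will be compared.
- Section 1 calls these comparisons exploratory, and the objectives paragraph of Section 11 calls them tertiary.

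**The concern.** With the total fixed at 40, a more balanced split detects a smaller effect, so a row with one value for three different splits needs explaining. For 16/24 and 20/20 the table also moves from 1.2 at 80% power to 1.4 at 85%, which is a large step for five points of power.

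The effect is left in SD units, whereas Table 1 gives points. A reader therefore cannot see how big the difference behind the 85% figure is on the Ki-67 scale. The 85% sentence also names tumor grade, and groups whose sizes are not known in advance, while Table 2 has only two-group splits with at least 12 of 40 in the smaller group. What is at stake is how a non-significant group comparison will be read: the sentence as it stands could lend it more weight than the design gives it.

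**Working it through.** **Inputs.** Two-sided alpha 0.01 and SD 12 (Table 1 header, carried to Table 2 by the text between the tables); correlations 0.2, 0.5 and 0.8 (Table 1); baseline Ki-67 from 20 women, "mean percent positive Ki-67 was 11.0% with a standard deviation (SD) of 12" (percent); total of 40 in the three splits of Table 2.

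**Step 1: reproduce Table 1.** A one-sample noncentral t calculation at 85% power gives effect sizes 0.529, 0.560 and 0.597 for N = 50, 45 and 40, against the printed 0.53, .56 and .60. The SD of change is 12 × √(2(1 − r)):

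- r = 0.2: 12 × √1.6 = 15.18
- r = 0.5: 12 × √1.0 = 12.00
- r = 0.8: 12 × √0.4 = 7.59

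For N = 40 this gives 9.06, 7.16 and 4.53 points, which round to the printed 9, 7 and 5. Table 1 is sound, and it confirms that effect size is in units of the SD of change, with equal SDs before and after treatment.

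**Step 2: recompute Table 2.** Power of the two-group Kruskal-Wallis test (chi-square, 1 df, alpha 0.01) was simulated with normal data and interpolated.

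| Power | 12/28 printed → recomputed | 16/24 printed → recomputed | 20/20 printed → recomputed |
|---|---|---|---|
| 80% | blank → 1.30 | 1.2 → 1.20 | 1.2 → 1.17 |
| 85% | 1.4 → 1.37 | 1.4 → 1.27 | 1.4 → 1.24 |
| 90% | 1.5 → 1.46 | 1.5 → 1.35 | 1.5 → 1.33 |

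The 12/28 column and the 80% row reproduce. The other four cells do not. A noncentral t calculation with the rank-test efficiency for normal data (3/π) gives 1.34 / 1.25 / 1.23 at 85%, the same pattern.

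**Step 3: can rounding explain it?** Going from 80% to 85% power adds 1.27 − 1.20 = 0.07 SD for 16/24 and 1.24 − 1.17 = 0.07 SD for 20/20. The smallest gap that could round to 1.2 and 1.4 is 1.35 − 1.25 = 0.10. Alphas of 0.005, 0.02 and 0.05 and the lower-bound efficiency of 0.864 were also tried. None gives both 1.2 at 80% and 1.4 at 85% for one split.

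**Step 4: direction of the error.** At 1.4 SD the simulated power is 87% / 92% / 93% for 12/28, 16/24 and 20/20. The printed cells overstate the detectable effect.

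**Step 5: convert to Ki-67 points.** 1.4 × 7.59 = 10.6 (r = 0.8); 1.4 × 12.00 = 16.8 (r = 0.5); 1.4 × 15.18 = 21.3 (r = 0.2). If both groups start at the pooled mean of 11, complete loss of Ki-67 in one and no change in the other is a difference of 11 − 0 = 11 points. The 1.4 SD effect exceeds this at r = 0.5 and r = 0.2 and falls just inside it at r = 0.8. The smallest recomputed 85% effect (1.24, for 20/20) is 9.4, 14.9 and 18.8 points at r = 0.8, 0.5 and 0.2, so the picture is the same.

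**Step 6: groups outside Table 2.** The documents give no group prevalences, so these splits of 40 are assumptions. At 1.4 SD the simulated power is about 72% for 8/32 and 56% for 6/34. For three grades at 10/20/10, equally spaced with 1.4 SD between lowest and highest, it is about 45%.

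**The case against.** The strongest reply is that the 85% statement is true where Table 2 applies. It is claimed only for large effects, and 1.4 SD reaches at least 85% in all three splits with normal data. The sample size rests on feasibility, the comparisons are exploratory and tertiary, and confidence intervals are already planned. All of this stands, and it keeps the point modest.

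Three stronger readings are tempting, and the documents support none of them.

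- A reader might infer that the 85% power is illusory. It is not: the flat rows understate power for 16/24 and 20/20.
- A reader might take 11 points as a hard ceiling. That needs both groups to start at the pooled mean and neither to rise. Only a pooled mean from 20 women is given, and baselines may differ by grade or receptor status.
- A reader might build a power scenario from the cited atorvastatin study in Section 2c: "there was a 7.6% reduction in Ki67 expression with a higher reduction of 68% noted among breast tumor samples". The 7.6% is the overall reduction and the 68% belongs to tumors with high HMGCoAR expression. The plan reports no low-expression comparator, so the two figures are not a between-group contrast.

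The exploratory label does not, however, correct wrong cells, put the effect on the Ki-67 scale, or extend Table 2 to grade or smaller groups.

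**Conclusion.** The point holds as a correction to stated design figures. Four cells of Table 2 are wrong on the plan's own assumptions: those for 16/24 and 20/20 at 85% and 90%, which overstate the detectable effect by about 0.13 to 0.17 SD. The 80% cell for 12/28 is blank and should be about 1.30. The fault is conservative and does not undermine the 85% power at 1.4 SD.

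The more useful finding is about scale and coverage. At low to moderate correlation the tabulated effect is larger than complete loss of Ki-67 in one group against no change in the other, if both start at 11. The 85% sentence also takes in a grade comparison and possible small groups for which the table shows nothing.

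The figures assume normal data and equal pre and post SDs of 12. Logistic data give 90% / 94% / 96% power at 1.4 SD. Short-tailed uniform data give 82% for 12/28 and at least 88% for the other two splits. That the 12/28 values were copied across the rows is a guess; the documents do not show how the cells arose.

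**What to change.** 1. Replace Table 2 with two-decimal values for 12/28, 16/24 and 20/20: 1.30 / 1.20 / 1.17 at 80%, 1.37 / 1.27 / 1.24 at 85% and 1.46 / 1.35 / 1.33 at 90%. Do not round down to one decimal: for 20/20, 1.2 has only about 82% power and 1.3 about 88%, so both would miss their row.
2. Add the equivalent Ki-67 points at correlations 0.2, 0.5 and 0.8. For the 85% row these are 20.8 / 16.4 / 10.4 for 12/28, 19.3 / 15.2 / 9.6 for 16/24 and 18.8 / 14.9 / 9.4 for 20/20.
3. Limit the 85% sentence to two-group splits with at least 12 of 40 in the smaller group and to differences of the tabulated size. Say that smaller groups and a three-level grade comparison have less power, with the 8/32 and 10/20/10 figures as labelled assumptions, and state how many grade levels will be compared.
4. Keep the planned Kruskal-Wallis tests and 95% confidence intervals as exploratory. Add that a non-significant group comparison is not evidence of equal effect.

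The cost is one recalculated table and a more qualified power statement. The corrected cells look slightly more favourable, while the wording around them becomes more cautious. No patients, samples or tests are added.
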